### **6.3.3 Variables**

The following variables will be collected for each AE:

- AE (verbatim)
- Date and time when the AE started and stopped
- Maximum intensity (mild, moderate, or severe)
- Whether the AE is serious or not
- Investigator causality rating against the investigational product (yes or no)
- Action taken with regard to investigational product
- AE caused subject's withdrawal from study (yes or no)
- Outcome

In addition, the following variables will be collected for SAEs:

- Date AE met criteria for serious AE
- Date investigator became aware of serious AE
- AE is serious due to
- Date of hospitalization
- Date of discharge
- Probable cause of death
- Date of death
- Autopsy performed
- Causality assessment in relation to study procedure(s)
- Description of AE

The investigator will rate the intensity of AEs using the following scale:

- mild (awareness of sign or symptom, but easily tolerated)

- moderate (discomfort sufficient to cause interference with normal activities)
- severe (incapacitating, with inability to perform normal activities)

It is important to distinguish between serious and severe AEs. Severity is a measure of intensity whereas seriousness is defined by the criteria in Section 6.2. An AE of severe intensity need not necessarily be considered serious. For example, nausea that persists for several hours may be considered severe nausea, but not an SAE unless it meets the criteria shown in Section 6.2. On the other hand, a stroke that results in only a limited degree of disability may be considered a mild stroke but would be an SAE when it satisfies the criteria shown in Section 6.2.

#### **6.3.4 Causality collection**

The investigator will assess causal relationship between investigational product and each AE, and answer “yes” or “no” to the question “Do you consider that there is a reasonable possibility that the event may have been caused by the investigational product?”

For SAEs, causal relationship will also be assessed for other medication and study procedures. Note that for SAEs that could be associated with any study procedure the causal relationship is implied as ‘yes.’

For a guide to the interpretation of the causality question, see Appendix A.

#### **6.3.5 Adverse events based on signs and symptoms**

All AEs spontaneously reported by the subject or reported in response to the open question from the study personnel: “Have you had any health problems since the previous visit?” or revealed by observation will be collected and recorded in the eCRF. When collecting AEs, the recording of diagnoses is preferred (when possible) to recording a list of signs and symptoms. However, if a diagnosis is known and there are other signs or symptoms that are not generally part of the diagnosis, the diagnosis and each sign or symptom will be recorded separately.

#### **6.3.6 Adverse events based on examinations and tests**

The results from protocol-mandated laboratory tests and vital signs will be summarized in the clinical study report. Deterioration as compared to baseline in protocol-mandated laboratory values, vital signs, and ECGs should therefore only be reported as AEs if they fulfill any of the SAE criteria or are the reason for discontinuation of treatment with the investigational product.

If deterioration in a laboratory value/vital sign/ECG is associated with clinical signs and symptoms, the sign or symptom will be reported as an AE and the associated laboratory result/vital sign will be considered as additional information. Wherever possible, the reporting investigator uses the clinical, rather than the laboratory term (eg, anemia versus low hemoglobin value). In the absence of clinical signs or symptoms, clinically relevant deteriorations in non-mandated parameters should be reported as AE(s).

Any new or aggravated clinically relevant abnormal medical finding at a physical examination as compared with the baseline assessment will be reported as an AE.

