### **3.9 Discontinuation of investigational product**

Subjects may be discontinued from investigational product in the following situations, at the discretion of the investigator(s):

- Subject decision. The subject is at any time free to discontinue treatment, without prejudice to further treatment.
- An AE that in the opinion of the investigator warrants subject withdrawal.
- Severe non-compliance with the study protocol.
- Withdrawal of informed consent.
- CK >10 x ULN accompanied by muscle pain, tenderness, or weakness; see Appendix D for management of increased creatine kinase.
- ALT or AST >3 x ULN; see Appendix C for further instruction on cases of increases in liver biochemistry and evaluation of Hy's Law.
- Deterioration in the subject's condition that in the opinion of the investigator warrants subject withdrawal.
- At investigator's discretion.
- Development of a condition that made the subject high-risk, such as clinical atherosclerotic disease (MI, transient ischemic attack, stroke, angina pectoris, symptomatic CAD, peripheral arterial disease, abdominal aortic aneurysm) or diabetes mellitus.

Subjects will be monitored to ensure that they are within the entry criteria limits for LDL-C throughout the study. Subjects will be discontinued from the treatment in 1 of 2 circumstances based on a subject's inclusion criteria:

1. Subjects with no additional CVD risk factors other than age and hypertension, and subjects without hypertension who have 3 or more other risk factors (including age) will be discontinued from the treatment if their LDL-C levels are  $\geq 160$  mg/dL (4.1 mmol/L) on 2 consecutive visits during the study.
2. Subjects without hypertension who have fewer than 3 other risk factors (including age) will be discontinued from the treatment if their LDL-C levels are  $\geq 190$  mg/dL (4.9 mmol/L) on 2 consecutive visits during the study.

The results of the LDL-C determinations will remain unblinded to the central laboratory but will be blinded to the investigator and site personnel after screening. A flag on the central laboratory report will notify the investigator that the subject should be removed from the study. The subject will be discontinued from the study and complete the Early Termination visit procedures. Subsequent treatment will be advised by the investigator based on local guidelines.

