### 5.1.2 Lipid parameters

Blood samples for analysis of lipid parameters will be collected at the times indicated in the Study Plan shown in [Table 1](#).

Subjects must fast for at least 8 hours and must have been sitting for at least 5 minutes before blood samples are taken for lipid assays. If a subject attends a study visit without having fasted for 8 hours, he or she must be asked to return at another time within the visit window for the study visit.

The central laboratory will provide the investigational sites with all the appropriate materials for specimen collection and sample processing, packaging, and shipping to the central laboratory. A central laboratory manual providing detailed instructions will be provided to each investigational site before trial start.

The principal investigator will ensure that samples are labelled and shipped in accordance with the Laboratory Manual and the Biological Substance, Category B Regulations (materials containing or suspected to contain infectious substances that do not meet Category A criteria), see Appendix B. Any samples identified as Infectious Category A materials are not to be

shipped, and no further samples will be taken from the subject unless agreed with AstraZeneca and appropriate labelling, shipment and containment provisions are approved.

Sample analysis will be carried out in the central laboratory.

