## **A GUIDE TO INTERPRETING THE CAUSALITY QUESTION**

When making an assessment of causality consider the following factors when deciding if there is a ‘reasonable possibility’ that an AE may have been caused by the drug.

- Time Course. Exposure to suspect drug. Has the subject actually received the suspect drug? Did the AE occur in a reasonable temporal relationship to the administration of the suspect drug?
- Consistency with known drug profile. Was the AE consistent with the previous knowledge of the suspect drug (pharmacology and toxicology) or drugs of the same pharmacological class? Or could the AE be anticipated from its pharmacological properties?
- De-challenge experience. Did the AE resolve or improve on stopping or reducing the dose of the suspect drug?
- No alternative cause. The AE cannot be reasonably explained by another aetiology such as the underlying disease, other drugs, other host or environmental factors.
- Re-challenge experience. Did the AE reoccur if the suspected drug was reintroduced after having been stopped? AstraZeneca would not normally recommend or support a re-challenge.
- Laboratory tests. A specific laboratory investigation (if performed) has confirmed the relationship.

In difficult cases, other factors could be considered such as:

- Is this a recognized feature of overdose of the drug?
- Is there a known mechanism?

Causality of ‘related’ is made if following a review of the relevant data, there is evidence for a ‘reasonable possibility’ of a causal relationship for the individual case. The expression ‘reasonable possibility’ of a causal relationship is meant to convey, in general, that there are facts (evidence) or arguments to suggest a causal relationship.

The causality assessment is performed based on the available data including enough information to make an informed judgment. With limited or insufficient information in the case, it is likely that the event(s) will be assessed as ‘not related’.

Causal relationship in cases where the disease under study has deteriorated due to lack of effect should be classified as no reasonable possibility.

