4.4.6 Adverse events leading to discontinuation

Number of subjects who discontinue during the screening phase due to an AE will be listed.

Treatment emergent AEs leading to study treatment discontinuation will be summarized by SOC, PT, and treatment group for safety analysis.

In addition, a subject listing of discontinuations due to AEs will be presented for screening and double-blind treatment period.

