4.5.1 Summary of laboratory variables over time

Descriptive statistics (number of observations, mean, SD, minimum, median and maximum values) for collected values, change from baseline, and percentage change from baseline will be summarized for clinical laboratory tests (hematology, chemistry, urinalysis, lipid profile) at each protocol scheduled nominal visit and at the last non-missing post-baseline visit, across treatment groups.

Hepatic biochemistry and CK values as well as their changes from baseline, plus change from baseline and percentage change from baseline in creatinine, will be summarised using descriptive statistics at each visit.

Hematology, hepatic biochemistry (including CK) and clinical chemistry values outside the laboratory reference ranges will be flagged and summarised.

Urinalysis data including pH and specific gravity will be summarised by mean, median, SD, minimum, maximum, and number of subjects for each treatment group at each visit.

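### Protocol 6.3.6 read with 3.9 lets LDL-C-triggered removals, which fall almost wholly on placebo, be recorded as AEs leading to discontinuation, and neither document exempts them

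*Protocol*

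**What the plan says.** **AE reporting.** Protocol 6.3.6 takes as its subject "Deterioration as compared to baseline in protocol-mandated laboratory values, vital signs, and ECGs" and says that these "should therefore only be reported as AEs if they fulfill any of the SAE criteria or are the reason for discontinuation of treatment".

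**LDL-C removal.** Protocol 3.9 sets two limits, 160 and 190 mg/dL, according to risk group. On 2 consecutive visits at or above the relevant limit, subjects are taken off treatment (the rule reads "will be discontinued from the treatment if their LDL-C levels are" followed by the limit). The site does not see the value: "A flag on the central laboratory report will notify the investigator that the subject should be removed from the study".

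**Status of lipids.** Protocol 5.1.2, under efficacy assessments, says "Blood samples for analysis of lipid parameters will be collected at the times indicated in the Study Plan". SAP 4.5.1 later names the lipid profile among "clinical laboratory tests (hematology, chemistry, urinalysis, lipid profile) at each protocol scheduled nominal visit".

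**Tabulation.** AEs leading to discontinuation are a named safety outcome (Protocol 2.3 and 8.4.3). SAP 4.4.6 states: "Treatment emergent AEs leading to study treatment discontinuation will be summarized by SOC, PT, and treatment group for safety analysis". SAP 4.4.2 also gives overall incidences of all AEs and of AEs leading to discontinuation by arm. Neither section sets lipid-triggered exits aside.

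**Lack of effect.** The causality guide in Protocol Appendix A says: "Causal relationship in cases where the disease under study has deteriorated due to lack of effect should be classified as no reasonable possibility".

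**The concern.** LDL-C change is a secondary efficacy outcome. If failure to stay below an LDL-C limit is recorded as an AE that ended treatment, an efficacy difference enters a table that readers use to judge tolerability. The effect runs one way. An LDL-lowering drug keeps subjects under the limit and placebo does not, so the crude totals would make rosuvastatin look better tolerated than it is.

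The documents also leave room for different practice. One site may enter an AE and another only a withdrawal reason. With 25 sites, the total could mix the two conventions with no way to tell from the table which was used.

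**Working it through.** **1. The chain in the text.**
- Protocol 6.1 counts abnormal investigation results, including laboratory findings, as possible AEs.
- Section 6.3.6 keeps worsening in protocol-mandated laboratory values out of AE reporting, with two exceptions. One is that the worsening is why treatment was stopped.
- The serum lipid profile is scheduled in Table 1, so LDL-C is protocol-mandated. Section 6.3.6 is not limited to the safety panel in Table 2.
- Section 3.9 makes LDL-C the reason for stopping.
- Section 6.3.3 collects, for each AE, the action taken with study drug and whether it caused withdrawal. The record then feeds SAP 4.4.2 and 4.4.6.
- The Appendix A wording settles causality only. It keeps the event out of the related-AE tables (SAP 4.4.5) but not out of the other two.

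**2. Size.** The plan gives no removal rate, so there is no figure to reproduce. Inputs:

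| Input | Value | Source |
|---|---|---|
| Randomized, ratio | 543, 1:1, so 543/2 = 271.5; 271 used | Protocol synopsis, 3.3 |
| Entry range | 120 to <160 or 120 to <190 mg/dL | Protocol 3.1 |
| Lipid tests used | Weeks 6, 13, 39, 65, 91 | Protocol Table 1 |
| Usual LDL-C | mean 135 to 145, SD 25 mg/dL | assumed |
| Within-person CV | 6 to 10% | assumed |
| Change on treatment | placebo 0, rosuvastatin −40% | assumed |
| Risk-group mix | half at each limit | assumed |
| Recording | every qualifying removal entered as an AE | assumed |

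Each measured value is the usual level × (1 + error). A subject enters on one qualifying value, and a separate Week 0 value is drawn. Removal is the first pair of successive lipid results at or above the limit. It meets the 6.3.6 condition only if the triggering value exceeds Week 0.

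Expected placebo count = 271 × (rate at 160 + rate at 190) / 2.

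| Definition | Low end | High end |
|---|---|---|
| Every removal | 271 × (0.0858 + 0.0120)/2 = 13.3 | 271 × (0.1925 + 0.0404)/2 = 31.6 |
| Removal and above Week 0 | 271 × (0.0635 + 0.0095)/2 = 9.9 | 271 × (0.1420 + 0.0325)/2 = 23.6 |
| Same, adjacent visits only (Weeks 6 and 13) | 271 × (0.0283 + 0.0037)/2 = 4.3 | 271 × (0.0636 + 0.0122)/2 = 10.3 |

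The last row matters because Visits 7, 9 and 11 have no lipid test. If consecutive means adjacent in the visit schedule, Weeks 6 and 13 are the only post-baseline pair before Week 104. The documents do not say which reading applies. Simulated rosuvastatin removals were about 0 throughout.

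**3. Effect on a crude total.** Let p be the true AE-discontinuation rate in both arms and q the placebo rate of qualifying LDL-C exits. The placebo rate shown is p + q(1 − p), so the artificial difference is q(1 − p).
- 10 to 24 of 271 is q = 3.7% to 8.9%. 4 to 10 of 271 is q = 1.5% to 3.7%.
- With p = 5% (assumed) and q = 3%: 0.05 + 0.03 × 0.95 = 0.0785. The table shows 7.9% against 5.0%, a ratio of 0.64, where the true ratio is 1.
- For p from 3% to 8% and q from 1% to 10%, the difference runs from 0.01 × 0.92 = 0.9 points to 0.10 × 0.97 = 9.7 points.

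**The case against.** The strongest reply is that 6.3.6 was never meant for lipids. They sit under efficacy in Protocol 5.1, while the safety laboratory panel in 5.2.1 and Table 2 contains none. The Table 2, ECG and vital-sign sections each refer the reader to 6.3 for AE recording; the lipid section does not. Section 6.3.6 is phrased as a limit on reporting. Section 3.9 lists withdrawal for an AE separately from the LDL-C rule. Sites see a flag and not a value, so they may have no basis for entering a laboratory AE. SAP 4.2.1 already reports reasons for discontinuation by arm, and the eCRF codes are not in these documents, so a suitable reason may exist.

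Much of this stands. It shows that practice may differ between sites, and it rules out the inference that every removal has to become an AE. It does not supply an exemption: the words of 6.3.6 cover mandated laboratory values generally. Blinding does not break the chain either, because the flag tells the site that LDL-C has reached a limit the subject was below at screening.

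Two further points stand. Safety is descriptive, so no test or error rate is affected. The tables by preferred term and the subject listings would show lipid terms in their own rows, where a careful reader can separate them.

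**Conclusion.** The concern holds as a gap in the reporting rules that can bias two crude totals: all AEs and AEs leading to discontinuation. The direction follows from the documents, since Protocol 1.1 describes rosuvastatin as effective at lowering LDL-C; a non-adherent rosuvastatin subject could be an exception. The size is illustrative: roughly 10 to 24 placebo subjects, or about 4 to 10 on the narrower reading of consecutive visits, against about none on rosuvastatin. It rests on the assumed LDL-C distribution, CV, risk-group split and complete recording as AEs.

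A reader might go further in two ways. One is to count every simulated removal (about 13 to 32). That ignores the requirement in 6.3.6 that the value be worse than baseline. The other is to conclude that a real excess of intolerance on rosuvastatin would be cancelled or reversed. That could happen only in a crude total; excesses in other preferred terms would still appear in their own rows. Related-AE tables and the efficacy analyses are untouched. The change is worth making because it is cheap and the bias runs in one direction in a named safety outcome.

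**What to change.** - **Protocol 6.3.6:** state that meeting the section 3.9 LDL-C criterion is not by itself an AE. Symptoms or other findings remain reportable as now.
- **SAP 4.2.1:** report these removals by arm as their own discontinuation reason. If the eCRF already has such a reason, name it.
- **SAP 4.4.2 and 4.4.6:** present total AEs and AEs leading to discontinuation both with and without events whose only basis is that criterion. Identify those events before unblinding, from the preferred term and the laboratory flag. Protocol 8.1 allows SAP amendments until then.

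The discontinuation rule is left as it stands, and no visit or test is added. The cost is a sentence in the protocol, some SAP wording, possibly one eCRF code, and one extra table row or version.

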### 6.3.7 Hy's Law

Cases where a subject shows elevations in liver biochemistry may require further evaluation and occurrences of AST or ALT  $\geq 3$  x ULN together with total bilirubin  $\geq 2$  x ULN will need to be reported as SAEs. See Appendix C for further instruction on cases of increases in liver biochemistry and evaluation of Hy's Law.

## 6.4 Reporting of serious adverse events

All SAEs have to be reported, whether or not considered causally related to the investigational product, or to the study procedure(s). All SAEs will be recorded in the eCRF.

If any SAE occurs in the course of the study, then investigators or other site personnel inform the appropriate AstraZeneca representatives within 1 day (ie, immediately but **no later than 24 hours**) of when he or she becomes aware of it.

The designated AstraZeneca representative works with the investigator to ensure that all the necessary information is provided to the AstraZeneca Patient Safety data entry site **within 1 calendar day** of initial receipt for fatal and life-threatening events **and within 5 calendar days** of initial receipt for all other SAEs.

For fatal or life-threatening AEs where important or relevant information is missing, active follow-up is undertaken immediately. Investigators or other site personnel inform AstraZeneca representatives of any follow-up information on a previously reported SAE within 1 calendar day (ie, immediately but **no later than 24 hours**) of when he or she becomes aware of it.

Once the investigators or other site personnel indicate an AE is serious in the WBDC system, an automated email alert is sent to the designated AstraZeneca representative.

If the WBDC system is not available, then the investigator or other study site personnel reports an SAE to the appropriate AstraZeneca representative by telephone.

The AstraZeneca representative will advise the investigator/study site personnel how to proceed.

## 6.5 Overdose

There is no specific antidote to rosuvastatin.

Experience of an overdose with other statins is limited; a few cases of an overdose following simvastatin have been reported. In all cases, there were no sequelae. Monitoring of CK and liver enzymes (ALT, AST) is recommended. Clinical monitoring and general supportive measures should be given as appropriate.

- An overdose with associated AEs is recorded as the AE diagnosis/symptoms on the relevant AE modules in the eCRF and on the Overdose eCRF module
- An overdose without associated symptoms is only reported on the Overdose eCRF module

If an overdose on an AstraZeneca investigational product occurs in the course of the study, then the investigator or other site personnel inform appropriate AstraZeneca representatives immediately, or **no later than 24 hours** of when he or she becomes aware of it.

The designated AstraZeneca representative works with the investigator to ensure that all relevant information is provided to the AstraZeneca Patient Safety data entry site.

For overdoses associated with an SAE, the standard reporting timelines apply; see Section 6.4. For other overdoses, reporting must occur within 30 days.

## 6.6 Pregnancy

All pregnancies and outcomes of pregnancy should be reported to AstraZeneca.

### 6.6.1 Maternal exposure

If a subject becomes pregnant during the course of the study, the investigational product should be discontinued immediately.

Pregnancy itself is not regarded as an AE unless there is a suspicion that the investigational product under study may have interfered with the effectiveness of a contraceptive medication. Congenital abnormalities/birth defects and spontaneous miscarriages should be reported and handled as SAEs. Elective abortions without complications should not be handled as AEs. The outcome of all pregnancies (spontaneous miscarriage, elective termination, ectopic pregnancy, normal birth or congenital abnormality) should be followed up and documented even if the subject was discontinued from the study.

If any pregnancy occurs in the course of the study, then the investigator or other site personnel informs the appropriate AstraZeneca representative within 1 day (ie, immediately but **no later than 24 hours**) of when he or she becomes aware of it.

The designated AstraZeneca representative works with the investigator to ensure that all relevant information is provided to the AstraZeneca Patient Safety data entry site within 1 or 5 calendar days for SAEs (see Section 6.4) and within 30 days for all other pregnancies.

The same timelines apply when outcome information is available.

The PREGREP module in the eCRF is used to report the pregnancy and the PREGOUT is used to report the outcome of the pregnancy.

